7.3.2.1 Prior to 3 months eVisit following ROBUST Surgery

• Subjects who have any subsequent surgery on either hand during the first 3 months following their procedure will be withdrawn from the study.

7.3.2.2 After 3 months eVisit :

- Subjects Treated with Unilateral CTR-US in ROBUST
 - Surgery in the Contralateral Hand Subjects who have subsequent surgery on the contralateral hand (i.e., non-study hand), including CTR, will not be involuntarily withdrawn from the study. Note that a subsequent CTR-US in the contralateral hand is still not eligible for enrollment in ROBUST.
 - Surgery in the Study Target Hand
 - Subjects who have subsequent surgery on the ROBUST hand that includes the wrist or carpal tunnel region, metacarpals, or thumb (with the exception of trigger thumb release) will be withdrawn from the study.
 - Subjects who have subsequent finger surgery (including trigger finger release) or trigger thumb release that does not affect the wrist or carpal tunnel region will not be withdrawn from the study

• Subjects Treated with Simultaneous Bilateral CTR-US in ROBUST - Subjects who have subsequent surgery on either hand that includes the wrist or carpal tunnel region, metacarpals, or thumb (with the exception of trigger thumb release) will be withdrawn from the study.

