In recent years, multiple studies have demonstrated the feasibility of using ultrasound to perform CTR through even smaller incisions while maintaining or even improving visualization of the carpal tunnel region, including its at-risk neurovascular structures. During CTR with ultrasound guidance (CTR-US), the carpal tunnel is typically accessed through a single small wrist or palmar incision <5 mm length and the TCL is transected using a small knife or similar cutting instrument while the carpal tunnel structures are continuously monitored visually using US. To date, a total of 22 clinical studies have been published reporting results on over 2,100 hands in over 1,650 patients at up to 2 years post-treatment comparing recovery time, effectiveness, and safety in subjects with CTS treated with CTR-US or mOCTR with US guidance $^{20-32}$. Among these over 2,100 hands, there were no major neurovascular complications, and the clinical success rate was >95%.

Historically, CTR procedures were performed in a hospital or an ambulatory surgery center (ASC). However, due to advancements in technology, greater patient demand, and concerns about growing healthcare costs, there is a distinct trend from performing CTR procedures in a hospital or ASC to an office-based setting. A recently published prospective single-center study demonstrated the feasibility of CTR-US when performed in an office-based setting ^{33.} The

improvement in CTS symptoms following office-based CTR-US was statistically significant and clinically important over 1 year of follow-up and no intraoperative complications or reoperations were reported. However, it remains unclear whether these results are reproducible across multiple practices treating patients with office-based CTR-US in real-world practice. Thus, the objective of this prospective multicenter trial is to evaluate the safety and effectiveness of office-based CTR-US in a large cohort of patients (n=140) with symptomatic CTS followed for 2 years post-treatment.

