Mean BCTQ-SSS scores decreased by 1.2 (SE 0.07) points at 2 weeks, 1.3 (SE 0.07) points at 1 month, 1.6 (SE 0.09) points at 3 months, and 1.7 (SE 0.08) points at 1 year (p<0.001 at each follow-up interval). Mean BCTQ-FSS scores decreased by 0.6 (SE 0.06) points at 2 weeks, 0.9 (SE 0.07) points at 1 month, 1.1 (SE 0.07) points at 3 months, and 1.2 (SE 0.07) points at 1 year (p<0.001 at each follow-up interval). Mean QDASH scores decreased by 14 (SE 2) points at 2 weeks, 23 (SE 2) points at 1 month, 27 (SE 2) points at 3 months, and 32 (SE 2) points at 1 year (p<0.001 at each follow-up interval). No neurovascular injuries, tendon injuries, infections or significant post-surgical wound complications occurred, and there were no recurrences or reoperations reported in the study. One patient developed complex regional pain syndrome without evidence of nerve injury, which was promptly recognized and successfully treated. This patient ultimately had CTR-US performed on the contralateral hand.

The purpose of this prospective multicenter study is to determine the safety and effectiveness of CTR-US when performed in an office setting.

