7.3 SUBJECT WITHDRAWAL FROM STUDY

7.3.1 Voluntary Withdrawal

A subject may voluntarily withdraw from the study at any time. If a subject officially withdraws from the study, the investigator must ensure that the reason for the withdrawal is documented. If the subject had an AE, the subject should be followed until the resolution of the AE, if possible. Data from these subjects will be included in the analysis up to the point of each subject's withdrawal.

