7.3.2 Involuntary Withdrawal

A subject also may be withdrawn by the investigator if the investigator determines that continued subject participation in the study will have a negative effect on the safety of the subject. Data obtained up to the date of subject withdrawal will be included in the study.

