7.3.3 End of Study

Subjects may exit the study at the end of the study (i.e., the study is discontinued by the Sponsor) or when the subject has completed the 24-month follow-up visit, whichever comes first, unless the subject opted to find an alternative treatment.

An End of Study CRF will be completed at the time the study is completed, discontinued, or lost to follow-up for each subject.

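### A carpal tunnel revision of a treated hand forces withdrawal, so scheduled ePRO and adverse event follow-up stops for the clearest treatment failures, and section 8 names no revision outcome (minor, cheap to improve)

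*Combined protocol and SAP*

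**What the plan says.** - **Before the 3-month eVisit (7.3.2.1).** Subjects who have any operation on either "hand during the first 3 months following their procedure will be withdrawn from the study".
- **After it (7.3.2.2).** For unilateral cases the withdrawal rule covers "Subjects who have subsequent surgery on the ROBUST hand that includes the wrist or carpal tunnel region, metacarpals, or thumb", and for simultaneous bilateral cases "Subjects who have subsequent surgery on either hand that includes the wrist or carpal tunnel region, metacarpals, or thumb". Trigger thumb release is exempt in both. Unilateral subjects are expressly kept after other finger surgery on the study hand and after contralateral surgery.
- **Data after involuntary withdrawal (7.3.2).** "Data obtained up to the date of subject withdrawal will be included in the study". Section 10.2.3 plans no imputation.
- **Outcomes (8.1 to 8.2.9).** BCTQ-SSS, the other scales and related adverse events run to 24 months. No revision, reoperation or treatment-failure outcome is named.
- **Objective (section 3).** Safety and effectiveness in patients "with symptomatic CTS followed for 2 years post-treatment".
- **What can still record the event.** 7.2.3 provides case report forms for unscheduled visits due to additional hand surgery, 7.3.3 an End of Study form, and 9.5 the action taken and outcome of each adverse event. Sections 9 and 9.8.1 place the list of adverse events on an eCRF that is not reproduced.
- **Loose ends.** 7.3.1 says of voluntary withdrawal: "If the subject had an AE, the subject should be followed until the resolution of the AE, if possible". 7.3.2 has no such sentence. The exit rule in 7.3.3 closes with "unless the subject opted to find an alternative treatment".

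**The concern.** A repeat release of a treated hand is the plainest sign that the procedure failed or led to a complication. Under these rules it is also the event that stops the data. In a single-arm trial the mean changes and event rates are the whole result, so a reader will want to know how many subjects needed revision and how they fared to 2 years. Section 8 commits to neither, although section 5 reports reoperation findings for both prior studies; of the office-based one it says "there were no recurrences or reoperations reported in the study".

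Two side effects follow. In simultaneous bilateral subjects, revision of one hand ends collection for the other treated hand, although 7.2.2 has BCTQ-SSS measured on all treated hands. And the early rule also removes subjects for unrelated or other-hand surgery, so the 3-month score of a hand that was not re-operated is never collected. That second kind of missingness is not driven by failure.

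**Working it through.** **Inputs**
- Enrolled 140, attrition 15%, SD of change 0.75 (10.1). Evaluable: 140 × 0.85 = 119.
- Registry (section 5): 1 incomplete release confirmed at reoperation among 346 patients with complication data, drawn from a 6-month cohort. 1/346 = 0.29%, matching the stated 0.3%.
- Office-based study (section 5): 88 patients with 1-year data and no reoperations, so 0/88.
- Illustrative improvement at 3 months: registry mean BCTQ-SSS 3.0 to 1.5, that is 1.5 points. MCID 1.14 (section 5).

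**Exact (Clopper-Pearson) 95% upper limits for the prior rates**
- 1/346: 1.60%.
- 0/88: 1 − 0.025^(1/88) = 4.11%.

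**Subjects whose follow-up would be cut short, and effect on the 3-month mean**

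Suppose a share f is revised before 3 months with no improvement, and the rest improve by 1.5. The mean over everyone is 1.5(1 − f) and the mean over those retained is 1.5, so the overstatement is 1.5f. The standard error is 0.75/√119 = 0.069.

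| Revision rate f | Expected in 140 | Chance of at least one, 1 − (1 − f)^140 | Overstatement 1.5f | In SE units |
|---|---|---|---|---|
| 1/346 | 0.4 | 33% | 0.004 | 0.06 |
| 1.60% | 2.2 | about 90% | 0.024 | 0.35 |
| 4.11% | 5.7 | 99.7% | 0.06 | 0.90 |

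The last two rows are ceilings, not forecasts. They apply 6-month and 1-year rates to a 3-month window, and they give no credit to the day-14 and 1-month scores, which remain in the longitudinal mixed model.

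**Distance from any change of conclusion**
- For the retained mean of 1.5 to hide a true mean below the MCID: 1.5(1 − f) = 1.14, so f = 0.24.
- Success is tested against zero change. The mean needed for significance is about 1.96 × 0.069 = 0.135, far below 1.5.

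**What is lost per subject.** Revision at month 3 forgoes 24 − 3 = 21 of the 24 months.

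**What a named rate would deliver, by the exact method already in 10.2.3**
- 0/140: 0 to 2.6%.
- 0/119: 1 − 0.025^(1/119), so 0 to 3.1%.
- 2/140: 0.2 to 5.1%.

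**The case against.** The withdrawal rule is evidently deliberate: it separates hands, periods and anatomical sites. Scores after a second operation no longer describe the study procedure alone, and other-hand surgery can confound MHQ, EQ-5D-5L and return to work. That stands as a reason to keep post-revision scores out of the main analysis. It is not a reason to stop collecting them, and the protocol already follows some subjects after later hand surgery.

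Three stronger readings are tempting, and the documents do not support them.

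- **That revisions vanish from the record.** The forms in 7.2.3, 7.3.3 and 9.5 allow the event to be captured. Adverse events recorded before withdrawal are retained, and incidence is per subject, so the loss is mainly later events of a new kind and later scores.
- **That no revision rate can come out of the plan.** The adverse event list is on an unseen eCRF. If reoperation is an item there, 10.2.3 already gives it a count, a percentage and an exact interval. All that can be said is that section 8 names no such outcome.
- **That 7.3.1 and 7.3.3 show failures being allowed to slip away.** The final clause of 7.3.3 is ambiguous, and 9.5 asks for resolution dates and outcomes without excepting withdrawn subjects. These are matters of wording to align.

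It is also fair that 1/346 is a confirmed incomplete release and is not stated as a total revision rate, and that the larger ceiling comes from a study with no events.

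**Conclusion.** The point holds as a minor one. Followed as written, the plan ends scheduled ePRO and adverse event follow-up for every subject whose treated hand is revised, and for the unrevised hand of a simultaneous bilateral subject, without naming a revision outcome in section 8.

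A reader might infer that the primary result is biased or the success claim unsafe. It is not: about 0.4 subjects and 0.004 points at the registry figure, and 2 to 6 subjects and 0.02 to 0.06 points at the illustrative ceilings. What suffers is the 6- to 24-month picture and the account of failures. There the mixed model leans on missing-at-random, which is doubtful when failure itself triggers withdrawal.

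The sizes rest on a 1.5-point improvement, on no change in revised hands, and on prior rates from cohorts limited to patients with follow-up data, at horizons of 6 months and 1 year.

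**What to change.** 1. **7.3.2.1 and 7.3.2.2.** Keep subjects with later hand surgery in remote ePRO and adverse event follow-up to 24 months unless they withdraw consent. Record the date, hand, anatomical site and reason of the surgery. Align 7.3.1, 7.3.2 and 7.3.3 with this.
2. **8.2.9.** Add the outcome: subjects with at least one revision surgery of a treated hand, at 3, 6, 12 and 24 months. Define revision as repeat carpal tunnel release, or wrist or carpal tunnel surgery for persistent or recurrent CTS or for a complication of the procedure. Report per subject (hands within a subject are correlated) the count, percentage and exact 95% interval, with the number observed to each time point as denominator. If the eCRF list already holds such an item, refer to it here.
3. **10.2.3.** Flag scores collected after a revision. Keep the planned 3-month analysis on pre-revision scores. Add two supporting analyses: one including the collected post-revision scores, one assigning no improvement to hands revised before 3 months. Show 6 to 24 months with and without post-revision scores. Retain the scores of unrevised treated hands.

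**Cost.** A protocol amendment with IRB review (11.9.2), the supporting analyses, and extra remote questionnaires for about 0.4 to 5.7 revised subjects. Subjects with unrelated or other-hand surgery in the first 3 months come on top. The documents give no rate for them; an assumed 1% to 5% would be 1.4 to 7 of 140, and exclusion 5 already removes planned contralateral procedures in that window. Some later scores will reflect a second operation, hence the reporting both ways.

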7.3.3 End of Study

Subjects may exit the study at the end of the study (i.e., the study is discontinued by the Sponsor) or when the subject has completed the 24-month follow-up visit, whichever comes first, unless the subject opted to find an alternative treatment.

An End of Study CRF will be completed at the time the study is completed, discontinued, or lost to follow-up for each subject.

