The median time to return to normal activities following CTR-US was 3 days (interquartile range [IQR]: 2-5 days), with 96.5% of patients reporting returning to normal activities within 2 weeks of the procedure. Among employed patients, the median time to return to work following CTR-US was 5 days (IQR: 3-9 days), with 92.3% of patients reporting returning to work within 2 weeks of the procedure. The median time to return to work based on employment type was 4 days (IQR: 3-6 days) for desk-based occupations, 6 days (IQR: 4-11 days) for light manual occupations, and 5 days (IQR: 3-14 days) for heavy manual occupations. The percentage of patients who were satisfied or very satisfied with the procedure was 91.6% at 2 weeks, 88.2% at 1 month, 88.0% at 3 months, and 89.8% at 6 months.

Among 346 (93%) patients with available complication data, no major neurovascular complications were reported. Specifically, there was 1 (0.3%) incomplete release confirmed

during reoperation and no reports of superficial infection, deep infection, arterial laceration, or permanent nerve injury.

A recent study by Bergum and Ciota ³³ demonstrated the feasibility of CTR-US when performed in an office-based setting. This was a prospective single-center study that evaluated 1-year outcomes in patients treated with office-based CTR-US. Among 88 patients (123 hands) with 1year follow-up data, 29 patients (57 hands) were treated with simultaneous bilateral procedures, 18 patients (25 hands) were treated with staged bilateral procedures, and 41 were treated with a unilateral procedure. All office-based procedures were successfully completed with local anesthesia and no intraoperative complications occurred.

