8. OUTCOMES

8.1 PRIMARY ENDPOINT

The primary endpoint of the study is BCTQ-SSS change at 3 months. The BCTQ is a CTS specific questionnaire that has been shown to be highly reproducible, internally consistent, valid, and responsive to clinical change in CTS and subject status post-CTR. The BCTQ includes a symptom severity score (BCTQ-SSS) and a functional status score (BCTQ-FSS). The BCTQ-SSS consists of 11 symptom severity questions. Scoring for the BCTQ- SSS ranges from 1 to 5, with higher scores indicating more severe symptoms, and is calculated as the mean of each response. The change in BCTQ-SSS score at the 3-month follow-up relative to baseline will represent the primary endpoint of the study.

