10.2.3 Data Analysis Methods

Baseline data will be analyzed using descriptive statistics. Continuous data will be summarized using mean and standard deviation for normally distributed data, median and interquartile range for non-normally distributed data, and counts and percentages for categorical data. For categorical variables, percentages will be calculated based on non-missing data.

The primary endpoint will be reported as the mean change in BCTQ-SSS at 3 months relative to baseline. Data will be reported as the mean change and 95% confidence interval. A linear mixed model will be the statistical test used to assess the primary endpoint, which accounts for the correlation inherent with bilateral procedures ⁴¹. The study will be deemed successful if the mean BCTQ-SSS score at 3 months is statistically significantly lower than at baseline, as determined by a p-value less than 0.05 using the linear mixed model.

Time to return to normal daily activities and time to return to work among employed individuals will be reported as the median and interquartile range in each treatment group.

Longitudinally measured continuous outcomes (i.e., BCTQ-SSS, BCTQ-FSS, MHQ, Numeric Pain Scale, EQ-5D-5L) will be analyzed using a linear mixed model.

Adverse events will be reported using counts, percentages and exact 95% confidence intervals using Clopper-Pearson's method. Calculation of AE incidence will be performed on a persubject basis.

Statistical analyses will be performed using a two-sided hypothesis test at a 5% level of significance. No adjustments for multiplicity are planned. Missing data imputation will not be performed. Subgroup analyses will be performed for subjects undergoing a unilateral or bilateral simultaneous procedure.

11.STUDY RESPONSIBILITIES AND MANAGEMENT

This study will be performed in accordance with all requirements set forth in the U.S. regulations, 21 Code of Federal Regulations (CFR) Parts 812, 50, 54, and 56, the Declaration of Helsinki, and any other applicable local laws, regulations, or guidelines.

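### Exit for alternative treatment (7.3.3) and withdrawal for early surgery (7.3.2.1) may selectively remove poor responders' 3-month scores and bias the reported mean improvement upward.

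*Combined protocol and SAP*

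**What the plan says.** Section 7.3.3 gives two ordinary end points for a subject, closure of the study by the sponsor or completion of the 24-month visit, and then adds an exception: "whichever comes first, unless the subject opted to find an alternative treatment". The clause does not define alternative treatment, does not say which hand or what period it covers, and does not say whether later scores are still sought.

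Three other rules bear on it:

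- Section 7.3.1: "A subject may voluntarily withdraw from the study at any time". For these subjects, "Data from these subjects will be included in the analysis up to the point of each subject's withdrawal".
- Section 7.3.2.1: subjects with any further surgery on either hand "during the first 3 months following their procedure will be withdrawn from the study".
- Section 7.3.2.2, which applies after the 3-month eVisit: unilateral subjects who have surgery on the other hand "will not be involuntarily withdrawn from the study". Surgery on a treated hand leads to withdrawal or not, depending on the site of the surgery.

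On analysis, Section 8.1 states: "The primary endpoint of the study is BCTQ-SSS change at 3 months". Section 10.2.3 uses a linear mixed model, justified by the correlation between hands in bilateral cases, and does not say which visits enter the primary model. It adds: "Missing data imputation will not be performed". No sensitivity analysis for missing 3-month scores is named.

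**The concern.** CTR-US is given once. A subject who leaves afterwards stops no study treatment; only data collection ends. Subjects who look for another treatment for the operated hand are likely to include those who have done badly, so the scores lost would tend to be poor ones.

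There is no control arm in which a similar loss could offset this. The main product of the trial is a mean change with a 95% confidence interval, and selective loss moves that mean in the favourable direction. Scores at 6 to 24 months and counts of related adverse events are exposed in the same way, because events after exit may go unrecorded.

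Sections 7.3.2.1 and 7.3.2.2 deal only with surgery. A non-surgical alternative, such as the splinting or injection listed among the nonsurgical options in the inclusion criteria, is treated as a reason for exit only by the clause in 7.3.3.

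**Working it through.** The plan gives no count or rate of exit for alternative treatment, so there is no plan figure to reproduce. The only loss figure is the overall 15% attrition in Section 10.1. What follows shows scale.

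**Inputs from the documents.** SD of the 3-month change 0.75 and attrition 15% (10.1); minimum enrolment 140, so 140 × 0.85 = 119 evaluable. Expected 3-month improvement: 3.0 − 1.5 = 1.5 in the registry and 1.6 in the office-based study (both Section 5).

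**Inputs assumed.** The share f lost before the 3-month score, 5-12%, and the shortfall D in their improvement compared with the rest, 0.5-1.5 points. The upper f is borrowed from the registry, where satisfaction was "88.0% at 3 months", so 100% − 88% = 12% were not satisfied. It is a ceiling for illustration and not an exit rate.

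**Shift in a completer mean.** If completers improve by m and those lost by m − D, the true mean is m − fD, so the completer mean is too high by f × D.

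| f | D = 0.5 | D = 1.0 | D = 1.5 |
|---|---|---|---|
| 5% | 0.025 | 0.05 | 0.075 |
| 12% | 0.06 | 0.12 | 0.18 |

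For comparison, the 95% CI half-width at 119 evaluable is 1.96 × 0.75/√119 = 0.135.

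**Ceiling on this.** If those lost were exactly the smallest improvers and change were normal, the shift would be SD × φ(z_f)/(1 − f):

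- 5%: 0.75 × 0.103/0.95 = 0.08
- 12%: 0.75 × 0.200/0.88 = 0.17
- 15%: 0.75 × 0.233/0.85 = 0.21

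The 0.18 corner of the table is therefore already at about the worst case that an SD of 0.75 permits.

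**What a mixed model with earlier visits would recover.** A simulation used the registry means and SDs (3.0, 1.7, 1.7, 1.5; 0.7, 0.6, 0.6, 0.6), a change SD of 0.75, assumed correlations of 0.5-0.7 among follow-up scores, a true change of 1.50, 15% lost, and an assumed log-odds slope of 1.5 per SD for dropout.

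| Dropout driven by | Completer mean | Mixed model, all visits |
|---|---|---|
| 1-month change (observed) | 1.59-1.61 | 1.50 |
| 3-month change (unobserved) | 1.63 | 1.54-1.56 |

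Using the earlier visits removes the bias that those scores explain. When dropout depends on the unseen score, 0.04-0.06 points remain.

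**Effect on the success criterion.** With 15% lost and completers averaging 1.5, the overall mean reaches zero only if those lost worsened by 1.5 × 0.85/0.15 = 8.5 points. From a baseline of 3.0 on a 1-5 scale the most possible is 2.0, which would leave 1.5 × 0.85 − 2.0 × 0.15 = 0.975.

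**The case against.** The strongest reply is that 7.3.3 opens no new door. Section 7.3.1 already allows withdrawal at any time, and 7.3.3 is permissive, so deleting the clause does not keep anyone in. This stands as far as it goes: the clause is not the sole cause of any loss, and the mandatory withdrawal in 7.3.2.1 is the firmer route. But a subject's right to leave differs from a protocol that names alternative treatment as a reason for exit and asks for no further scores.

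A reader might infer that 7.3.3 contradicts 7.3.2.2. It does not do so strictly, since declining to force a subject out is compatible with letting one leave. The two passages need aligning, and 7.3.2.2 in any case applies only after the 3-month eVisit.

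A reader might also take 12% as the share likely to exit. Satisfaction in the registry meant a score of 4 or 5, so the 12% includes neutral answers, and the registry report rests on the 373 patients who had 6-month follow-up. The nearest documented events are surgical: one reoperation among 346 patients, and none in the office-based study. At 1/346 = 0.3%, even D = 1.5 gives only 0.004 points. Non-surgical treatment is not quantified anywhere, so neither a small nor a large effect is established.

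Nor does seeking treatment always mark failure, because the clause does not confine it to the operated hand. Scores obtained after another treatment may also include its benefit, so keeping them does not by itself remove overstatement.

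**Conclusion.** The concern holds as a risk of upward bias in the reported mean. A reader might infer that the improvement *is* overstated. The documents do not support that: they give no number, timing or reasons for such exits.

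On the assumed ranges the shift in a completer mean is about 0.03-0.18 points against an expected 1.5-1.6. The upper part of that range is comparable to the 0.135 half-width. It is smaller if the primary model includes the 2-week and 1-month scores, which the plan leaves open. These figures rest on assumed f and D; the ceiling and simulation also assume normality, and the simulation further assumes a dropout mechanism and correlations. The success criterion, a test against zero, would not change. The point concerns the accuracy of the estimate and is worth correcting because the correction is cheap.

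**What to change.** 1. Delete the exception clause in 7.3.3. State that alternative treatment does not by itself end follow-up, and that questionnaire and adverse-event collection continue to 24 months unless the subject withdraws.
2. Record the type, hand and date of any alternative treatment.
3. Reconcile this with 7.3.2.1 and 7.3.2.2, so that scores are still collected after surgery where the subject agrees. Without this step the new sentence would conflict with the mandatory withdrawals. The change concerns data collection only, not clinical care.
4. State in 10.2.3 that the primary mixed model includes all scheduled visits.
5. Report the 3-month mean with and without scores obtained after alternative treatment. Which of the two is primary is an estimand choice that the plan should state.

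The cost is a small amendment, which Section 11.9.2 sends to the IRB, and a few CRF fields. The added burden is low: outcomes are collected remotely, and subjects have already agreed to 24 months of questionnaires.
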